First aid (FA) is very important for dealing with serious medical issues in order to help save lives, reduce pain, and support recovery. Anyone can provide first aid even young children as studies have shown us from the global North. Training programs have been effective in different places, including some African countries. It's important to include first aid training in schools to help young people learn how to protect themselves and their communities. The culture of First aid is almost nonexistent and just as adult lay first-responders have shown effective in the case of road traffic crashes. We want to ascertain the contribution of young children in learning and acquiring these skills and to raise a culture of alert young people in the face of conflict

The goal of this research is to understand how young people view first aid training and what obstacles they face in learning it. The study will focus on children aged 10 to 14 in Fako Division, Cameroon, aiming to improve their knowledge, attitudes, and practices (KAP) towards first aid. It will also look into the challenges of teaching first aid and its impact on children's health and safety.

The research will use a mix of methods, including surveys and interviews in two areas of Fako Division. One area will receive first aid training (the intervention group), while the other will not (the control group). Data will be collected through interviews, group discussions, and questionnaires, and then analyzed using specific software.

The study aims to identify problems that make it hard to teach first aid in schools and find

solutions to these issues. It is also expected that children's knowledge and skills related to first aid will improve, allowing them to respond better in emergencies.

ABSTRACT

Background/Justification: Initial care is paramount for acute medical conditions to preserve life, alleviate suffering, prevent further illness or injury and promote recovery. This initial care is called first aid (FA). Anyone in any situation, including oneself can initiate the act. Adult lay-first responder FA programs have shown effectiveness in curbing acute injury and illness even in some African nations. However, just like in the West, it is necessary to incorporate FA training in the school curricula of the young for self and community awareness raising and safeguarding of one's life.

Objectives: To gain insights into the perceptions and barriers surrounding a Young First Aiders' (YoFA) training program on trauma/injury first aid in both the school setting and the community in the Fako Division and to assess and measurably improve KAP of early SSC on trauma/injury FA using the YoFA training program in Fako Division. The research aims to determine the Knowledge, attitudes and practices (KAP) of FA, identify the challenges of implementing first aid training, evaluate its effectiveness, and assess its overall impact on the well-being of school children and the community among children aged 10 to 14 years in Fako division, Cameroon.

Methods: The study will employ a mixed-methods exploratory sequential approach, combining quantitative surveys and qualitative interviews in the Tiko and Buea health Districts of the Fako Division. It will incorporate cross-sectional surveys and an experimental intervention. One of the districts will be the intervention group and the other the control. The qualitative part will use in-depth interviews, Focused group discussions (FGDs) and scenario observations as data collection methods. While the quantitative part will use self-administered questionnaires. Following the qualitative data collection of stakeholders including parents, pretested adapted questionnaires will be administered to the children. Data will be analysed using Nvivo and R software to analyse qualitative and quantitative data respectively.

Expected Results: Identification of challenges that prevent FA from being implemented in schools, and understanding probable solutions to address these challenges. Additionally, we expect to increase the KAPs of children in early secondary school regarding FA aspects such as staying safe, calling for help, doing something, and stopping a bleed after building their self-efficacy during the training.

Keywords: First aid, injury/trauma, first aid training, first aid training in school children.

CHAPTER ONE

INTRODUCTION AND BACKGROUND

1.1 INTRODUCTION

In an increasingly unpredictable world, the ability to respond effectively to emergencies is a vital skill that can save lives and mitigate injuries. Among the most critical of these skills is first aid, which encompasses the immediate care provided to individuals experiencing injury or trauma before professional medical help arrives. Despite the importance of first aid knowledge, many young people lack adequate training, leaving them ill-equipped to handle emergencies that may occur in their daily lives. This gap highlights the urgent need for initiatives aimed at empowering youth with essential first aid skills. The "Young First Aiders (YOFA) Training Program" aims to address this need by equipping early secondary school children in the Fako Division with the basic knowledge and skills necessary to manage injuries and trauma effectively before professional help arrives at the scene or before a victim is transported to the closest health facility. By targeting this age group, the program seeks to instill a sense of responsibility and confidence in young individuals, enabling them to act decisively in emergency situations. The Fako Division, with its unique socio-economic landscape and diverse population, presents both challenges and opportunities for implementing such a program. This research proposal outlines the framework for implementing the YOFA Training Program, which will include comprehensive training modules and practical exercises, and community engagement initiatives. Through this program, we aspire to

not only enhance the first aid capabilities of young individuals but also to foster a culture of safety and preparedness within the community. This initiative represents a proactive approach to child and youth empowerment, ultimately contributing to a more resilient society capable of responding to emergencies with skill and compassion.

1.1.1 Conceptual Definitions

First aid: The European Resuscitation Council (ERC), during its 2020 International Consensus on Cardiopulmonary Resuscitation (CPR) Science with Treatment Recommendations, defined first aid as the preliminary or initial care given to someone with an acute illness or injury [1]. Other international bodies have included the need for care to be given until professional help arrives in the face of a sudden traumatic or debilitating health event [2]. Yet others like the Occupational Safety and Health Administration (OSHA) have included aspects of the aid being given at the location of the event, it being a one-time act, and requiring only little technology and training [3] to preserve life or prevent sequelae.

Youth Empowerment: The process of equipping young individuals with the skills, knowledge, and confidence necessary to take control of their lives and make informed decisions. In the context of the YOFA program, it refers to enabling children to act effectively in emergency situations [1].

Injury and Trauma: Refers to physical harm or damage to the body resulting from various causes, including accidents, falls, or violence. Trauma can be classified as either minor (e.g., cuts and bruises) or major (e.g., fractures or severe bleeding), necessitating different levels of first aid response [2,3].

Training Program: A structured educational initiative designed to impart specific knowledge and skills to participants. In this study, it refers to the YOFA program that

aims to teach early secondary school children essential first aid techniques and principles [4,5].

Emergency Response: The actions taken to address an urgent situation that poses a risk to health, life, or property. This includes the immediate steps taken by individuals trained in first aid to stabilize a person in distress until professional help arrives [6,7].

Skill Acquisition: The process through which individuals learn and master specific abilities or techniques. In the context of the YOFA program, it refers to the development of practical first aid skills among early secondary school children through hands-on training and practice.

These conceptual definitions provide a foundational understanding of the key terms and ideas that underpin the YOFA Training Program, facilitating a clearer focus for our objectives.

1.1.2 Operational Definitions

First Aid Knowledge: Measured by a standardized questionnaire assessing participants' understanding of basic first aid principles, including recognition of injuries, appropriate responses, and the use of first aid equipment. A pre-test and post-test will be administered to evaluate knowledge gained from the training.

Practical Skills Proficiency: Evaluated through hands-on assessments where participants (children) demonstrate specific first aid techniques, such as identification of injuries including wounds and take action towards care. Proficiency will be rated on a scale from 1 to 5 by the trainers based on accuracy and confidence in performing the skills.

Training Attendance: Defined as the percentage of scheduled training sessions attended by each participant. Attendance will be tracked through a sign-in sheet at each

session, with a minimum attendance threshold set at 80% to qualify for the evaluation phase.

Behavioral Intent to Use First Aid: Assessed using a Likert scale survey administered after the training program, measuring participants' self-reported likelihood of applying first aid skills in real-life situations. This will include scenarios where they might encounter injuries or emergencies.

Community Engagement: Measured by the number of community members who give favourable feedback on the activities of the YoFA trainees during and after the intervention. The effectiveness of these activities will be evaluated through feedback forms from community members.

Self-Efficacy in First Aid: Evaluated using a self-report scale that assesses participants' confidence in their ability to perform first aid tasks taught. This will be measured before and after the training program to determine changes in self-efficacy levels.

Injury Response Time: Measured by timing participants' responses in simulated emergency scenarios during training sessions. The time taken to initiate appropriate first aid measures will be recorded and analyzed to assess improvement over the course of the program.

These will help us ensure that the study effectively measures the impact of the YOFA Training Program on early secondary school children in the Fako Division, providing clear metrics for evaluation and analysis.

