1.6.2 Specific Objectives

1. To understand the perspectives of stakeholders (school teachers, administrators, parents, community leaders and students) on a school-based FA training (YoFA) program among SSC.

Hypothesis 1: The perspectives of stakeholders like school administrators, teachers, parents, community leaders, and school children needs to be understood to design a comprehensive YoFA program

2. To assess school children's Knowledge, Attitudes (willingness to) and Practices (self-efficacy) (KAP) on trauma/injury FA via the built YoFA training to stop LTBs.

Hypothesis 2: School children have limited knowledge, self-efficacy and practices regarding trauma/injury FA

3. To evaluate the effectiveness and usability of the YoFA training program for SSC to respond to LTBs safely and promptly in their environs.

Hypothesis 3: The YoFA training Program is effective in improving the KAP of SSC and it is usable within the school and community setting.

4. To determine the barriers associated with implementing the YoFA program among early SSC in the Fako Division.

Hypothesis 4: There exist some barrier/challenges in implementing a YoFA training

program in secondary schools.

CHAPTER TWO

LITERATURE REVIEW

It is important to understand some aspects regarding first aid training for children in schools. Here, we will be highlighting the relevance of Advanced Trauma Life Support concepts, the injury burden among school children, the qualifications of potential educators, and the appropriateness of school-based training. There is a clear consensus on the necessity and benefits of teaching first aid in schools, as it equips children with essential life skills, enhances their confidence, and promotes a safer environment. Future research should focus on developing effective training programs tailored to this age group, considering the emotional aspects of learning and the varied contexts in which children may need to apply their skills particularly in our setting.

First aid training is an essential aspect of emergency preparedness, particularly for children aged 10 to 14 years. This age group is increasingly exposed to various risks, both in schools and everyday life. Here, we will explore four key areas related to first aid training for children: the concept of Advanced Trauma Life Support (ATLS), the injury burden among school children, potential educators of first aid, and the appropriateness of implementing first aid training in schools.

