3.3.1 Qualitative Part

Discussions or interviews on perspectives of individuals and groups of individuals regarding the acceptability and usability of FA-trained kids within the school and in the community. It will also seek to understand their thoughts on incorporating an FA training program within the school curriculum. It will be conducted with key stakeholders, including school administrators, and community leaders as well as students of the school.

It will precede the qualitative part and include Focused group discussions (FGDs), in-depth interviews of certain community and administrative stakeholders within the school and observations of scenarios.

3.3.2 Quantitative Part:

The quantitative aspect will involve administering questionnaires to students to assess their knowledge, attitudes (confidence), and practices (utilisation/usability) of FA trauma/injury skills before and after their training. This will focus mostly on staying safe, calling for help and stopping a life-threatening bleed. The intervention will include training the intervention group in reasonable clusters on the same subject matter and assessing the change in KAPs before and after the intervention. It will also include scenarios to test the efficacy of participants in carrying out the First Aid Act.

PERIOD OF STUDY

The study will be a 10-month study from September 2024 to July 2025 including administrative and ethical clearance needed.

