will be a session for pretesting at the beginning of the intervention, at the immediate end, and 3 months after. **During the 3 months follow up period, we will visit the schools during their Wednesday club days every 2 weeks for 30mins to 1hour, to document their experiences and challenges in real time and their use of the skills.**

The qualitative part will take place before the quantitative pretesting of both groups begins.

Table 6: Plan of training and Evaluation of intervention groups

HA	School	N	Training Period in 2024	Date for Last Evaluation, 2024
Molyko (Intervention)	BGS Molyko	25	Nov 6 th , and 13 th	Feb 5 th
		25	Nov 20 th , and 27 th	Feb 19 th
		25	Dec 4 th and 11th	March 5 th
Mutengene (Control)	GHS Mutengene	70	November 6 th	Feb 26 th
	Total	145		

Step 3: Evaluation Phase

This comprises the evaluation of students' perceptions, barriers, and challenges in learning and applying the skills and lessons learned. It will equally involve evaluating parents' and stakeholders' perceptions about the program and including FA training in school curricula. It will involve the use of evaluation forms. This will take place about the same time as the post-three-month evaluation.

Knowledge will be assessed by evaluating whether the participants have ever heard of first aid or observed situations in which first aid was needed. They will be expected to have an increase in knowledge of first aid, especially regarding calling for help, stopping acute and life-threatening bleeds (LTB), and referrals after the training.

Before the training, we expect people not to have practiced first acts ever or to have

done it in a wrong way or to be scared to carry out specific first aid acts. After the training, we expect them to be more alert and identify situations needing first aid acts. Additionally, we expect their self-efficacy and confidence to perform first aid acts to increase and to effectively carry out first aid acts within their community or the school premises that will be documented using designed forms.

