3.7 STUDY VARIABLES AND TYPE

Variables

Outcome variables

1. Knowledge Change: to determine whether or not there was an overall change in knowledge before and after the training (dichotomous).
2. Test scores: to measure the educational efficacy of the first aid training before and after the intervention in comparison with the control group (continuous)
3. Self-efficacy ratings: Participants' self-perceived efficacy in performing first aid skills or their confidence levels in "Stopping the bleed and/or calling for help" (dichotomous)

4. Response time: The time taken by participants to respond to simulated first-aid scenarios or emergencies that require them to either stop an LTB or call for help or refer (continuous).
5. The number of participants who make use of the skills taught during the 3 months post-training but before the final assessment (Discrete).

Exposure Variables

The exposure variables include training on LTBs from injury first aid and the use of these services by the trained students (e.g., the number of persons assisted or referred during the follow up period of the training).

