3.8 DATA COLLECTION TOOLS

A) Questionnaire

**Pre- and Post-Implementation of a Young First Aiders (YoFA) Training
Program Amongst Early Secondary School Children on Injury and Trauma
First Aid in Fako Division.**

Health District _____
Secondary School _____

Date: _____
Class: _____

A) QUESTIONNAIRE

Section 1

Please answer the questions below by **ENCIRCLING OR WRITING** the right answer you think is correct. If you do not know an answer, please select the answer you think is correct.

1. Gender	YES	or	NO
2. Age (in years):	_____		
3. Parents' Occupation:	Father _____ Mother _____		
4. Do you have access to a mobile phone all the time?	YES	or	NO
5. Have you heard the words First Aid?	YES	or	NO
6. Have you ever seen a traumatic injury? (A traumatic injury is an injury you sustain when something outside your body causes you to lose function or render you unable to use part or all of your body because of pain, bleeding or the because it is very serious)	YES	or	NO
7. A) Have you ever received any training in First Aid (formal or informal)?	YES	or	NO
B) If yes, briefly describe the training (where was it, what did you learn? How long ago was it?)			
Where? _____			
How long ago?			

 a) < 6months ago b) 6 to less than 12 months ago c) 1 to 3 years ago d) >3 years ago 			
What you learnt? _____			
<hr/>			
8. Have you ever seen someone bleeding and tried to stop that bleed yourself at home, school, marketplace, or anywhere else?	YES	or	NO
B) How many times has that happened? (Choose one)			

 a) Never b) Just once c) 2 to 5 times d) >5 times 			

C) What did you do to stop the bleeding? _____ **YES** or **NO**

D) Did it work? **YES** or **NO**

9. **A) Do you remember watching other people do this in the past?** **YES** or **NO**
B) Have you ever watched someone else offer such help in question 5? **YES** or **NO**

10. **If you find someone bleeding today,** **YES** or **NO**

A) Will you help them?

B) If 'no', why will you not help?

- I don't know what to do
- I am afraid I will make it worse
- I am afraid I will get into trouble
- I am afraid of blood
- Other reason _____

C) If 'yes', why will you help? _____

D) What steps will you take to help if 'yes'?

- Help by putting in toothpaste
- Help by applying pressure on the wound
- I will not help
- I will call an elderly person.

[figure not shown]
B) If you would not help, what makes you not want to help?

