1 = Strongly Disagree with the statement made	2 = Disagree with the statement made	3 = Neutral you neither agree nor disagree to the statement made	4 = Agree with the statement made	5 = Strongly agree with the statement made
 1 ☆☆☆☆☆	 2 ★★☆☆☆	 3 ★★★★☆	 4 ★★★★☆	 5 ★★★★★

ITEM	Value per 5-point Likert scale response, n (%)				
	1	2	3	4	5
1. I feel that I can know what to do with the YoFA skills if I see someone in need					
2. I found the skills taught too complicated to use.					
3. I thought the skills were easy to use.					
4. I think that I would need help from the staff to be able to use these skills.					
5. I found the training topics in the YoFA skill set to be strongly related/closely associated to each other.					
6. I thought there were too many changes/ups and downs in the skill set taught					
7. I would imagine that most other children of my age would learn to use these skills very quickly.					
8. I thought the skills were really hard to use.					
9. I felt very confident using the skill set.					
10. I needed to learn a lot of things before I could start applying the skill set					

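### Self-efficacy is promised before and after training, but no visible item of the printed pre/post questionnaire measures it

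*Protocol*

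**What the plan says.** Section 1.1.2 defines self-efficacy as confidence in performing the first aid tasks, captured on a self-report scale, and adds: "This will be measured before and after the training program to determine changes in self-efficacy levels". The protocol relies on this measure in several other places:

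- Section 1.6.2, Objective 2, uses self-efficacy as the meaning of practices within KAP and willingness as the meaning of attitudes. Hypothesis 2 reads: "School children have limited knowledge, self-efficacy and practices regarding trauma/injury FA".
- Section 3.3.2 says the questionnaires assess knowledge, "attitudes (confidence), and practices (utilisation/usability) of FA trauma/injury skills before and after their training".
- Section 3.6, Step 3, states the expected effect: "we expect their self-efficacy and confidence to perform first aid acts to increase".
- Section 3.7 lists as outcome 3 the participants' "self-perceived efficacy in performing first aid skills or their confidence levels" and types it as dichotomous.
- Table 7 (3.11) gives the questionnaire as the tool for willingness and self-efficacy under Objective 2, with baseline KAP scores as the indicator.
- Section 3.11 analyses KAP change by difference-in-difference.

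Section 3.9 names three variables for the pre and post questionnaires: knowledge, practical skills and helping behaviour. Self-efficacy is not among them.

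On scenarios, section 1.1.2 times responses in simulations held in training sessions. The success criteria in section 3.6 count the students who do well in scenarios and then say that all these outcomes are compared between the groups. The control schedule in section 3.6 lists testing at the start, at the immediate end and at 3 months.

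**The concern.** A difference-in-difference needs the same measure before and after training in both arms. If the printed questionnaire is the one used, the pretest passes without a confidence rating, and that baseline cannot be recovered once training has begun. A listed outcome would then have no estimate as defined, and the self-efficacy part of Hypothesis 2, which is a statement about baseline, would have no direct evidence.

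The scenario issue is of the same kind but smaller. A between-group comparison is promised, and no control measurement is scheduled to supply it.

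**Working it through.** The protocol states no figure on this point. The check is a reading of the instruments in section 3.8 against what the analysis requires.

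**1. What the analysis requires.** For each post-test the estimate is (post − pre, trained) − (post − pre, control). That takes four cells. With two post-tests (immediate and 3 months) there are 2 arms × 3 occasions = 6 cells to fill.

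**2. What the pre/post questionnaire contains.**

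| Items | Content | Confidence or ability rating |
|---|---|---|
| 1–9 | background, past training and experience | 0 |
| 10 | willingness to help, reasons, steps | 0 |
| 11 | nearby health facilities | 0 |
| 12 | motivators | 0 |
| 13–18 | what to do, whom to call | 0 |
| 19–25 | recognising dangerous bleeding | 0 |
| 26–37 | tourniquet, pressure and packing | 0 |
| 38 | excitement about the training | 0 |

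Total: 9 + 1 + 1 + 1 + 6 + 7 + 12 + 1 = 38 items, of which 0 ask for a rating of confidence or ability.

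**3. The nearest items.**
- Item 10A is a yes/no on willingness, which Objective 2 and Table 7 name separately from self-efficacy.
- Item 10B asks why a child would not help. Of its 5 options, 2 bear indirectly on perceived ability: not knowing what to do, and "I am afraid I will make it worse". It follows a refusal in 10A, so a child who would help but feels unsure leaves no trace.
- Usability scale: 2 of 10 items are close, namely item 1 (knowing what to do) and item 9, "I felt very confident using the skill set". The scale is introduced as being about the skills learnt, so it has no meaning at pretest or in untrained controls.

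**4. Cells filled.** The questionnaire fills 0 of 6. The usability scale could fill at most the 2 post-training cells of the trained arm. The other 4 of 6 stay empty: both pretests and both control post-tests. Each difference-in-difference therefore has at most 1 of its 4 cells.

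**5. What cannot be seen.** Two figures in the questionnaire are not shown. One follows item 10D and is followed in turn by a stray sub-item B about not wanting to help, which suggests a lost part A. The other stands just before the bleed-recognition items. The wording of the stray B points to willingness rather than confidence, but this is an inference.

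**6. Scenarios.** Section 1.1.2 gives one setting for timed responses, the training sessions, which controls do not attend. The control schedule in section 3.6 names three test occasions and no scenario. The comparison promised in the success criteria therefore has no scheduled control measurement.

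**The case against.** Five arguments can be made against the point.

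- *The scale may exist elsewhere.* Section 1.1.2 does not say that it sits inside the questionnaire, and other tools, such as the intent survey and the feedback forms, are named but not printed in section 3.8. This stands in part: the supportable claim is that no printed instrument measures self-efficacy. But Table 7 assigns it to the questionnaire, and section 3.9 does not list it.
- *A figure may hide an item.* This cannot be excluded, which is why the count is of visible items.
- *It can be left to the analysis plan.* No analysis plan can supply a variable that was not collected.
- *Item 10B could be coded for every child.* Since section 3.7 makes the outcome dichotomous, refusal for lack of ability versus all others gives everyone a value. That is correct, but the result mixes confidence with willingness and counts a willing, unsure child as confident. It is a poor proxy and not the scale that was defined.
- *The effect is limited.* This stands. The KAP-change indicator for Objective 3 in Table 7 is knowledge scores.

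On scenarios, a reader might infer that sections 1.1.2 and 3.6 contradict each other. They do not. The first defines response time as a measure of progress during training. The second counts good performers in the evaluation phase, which section 3.2 opens to all students. The abstract and section 3.9 also place scenario observation or simulation among the qualitative methods, so scenarios are not confined to training. What remains is a gap in the schedule.

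**Conclusion.** The self-efficacy point holds. As printed, the instruments give this outcome no baseline and no control value: 0 of 38 visible questionnaire items, and 2 of 10 usability items usable only in trained children after training. Its difference-in-difference cannot be run. The conclusion rests on the printed questionnaire being the one administered and on the two missing figures not containing a confidence item.

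A reader might go further and infer that the whole KAP analysis fails. The documents do not support that. Knowledge scores and yes/no willingness are collected before and after, and the Objective 3 indicators in Table 7 do not depend on self-efficacy.

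The scenario point holds only as an unscheduled control measurement, and it is secondary.

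**What to change.** - Add a few confidence items to the questionnaire, for example one each on staying safe, calling for help and stopping a bleed. Word them without reference to the training, and use them at the pretest and both post-tests in both arms.
- Add self-efficacy to the variables listed in section 3.9.
- Align section 1.1.2 (a scale) with section 3.7 (dichotomous), stating the cut-off if a scale is to be dichotomised.
- Reconcile sections 1.1.2 and 3.6 on scenarios. The simplest way is to label response time as descriptive within the trained arm and to limit the between-group comparison to outcomes measured in both arms.

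Cost: three items at an assumed 20 to 30 seconds each take 3 × 20 = 60 to 3 × 30 = 90 seconds per sitting. Against the 30 minutes stated in section 3.12 that is 60/1800 = 3.3% to 90/1800 = 5.0%. No visit is added. The scenario change is wording only, and its price is a narrower between-group claim.

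If the pretest has already been given with the printed form, the baseline is lost. Neutral items at a remaining post-test would still allow a comparison of the arms, but it would not be a difference-in-difference and should not be reported as one.
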